	3.9.4 LATE CLINICAL SYMPTOMS	

1 Introduction

This document describes the content proposed for the primary statistical analysis of PREVAIL II, the randomized controlled trial of ZMapp in acute Ebola virus disease (EVD). The focus is on analyses that address the major randomized comparisons for key safety, tolerability and efficacy outcome measures, including those needed to address the study's primary objective as well as the main secondary objectives. This analysis plan therefore includes the key analyses for presentation or publication of the primary conclusions of the study.

2 Study Overview

The study protocol is a master protocol for the evaluation of multiple candidate countermeasures for the treatment of EVD. Given the waning epidemic, the initial (and, to date, only) phase of the trial was focused only on the evaluation of ZMapp, although the study was designed to provide flexibility to introduce additional treatments under certain situations that are described in the protocol. The Primary Objective of this study was to establish the safety and efficacy of ZMapp in patients diagnosed with Ebola virus infection.

Patients were randomized in the United States, Liberia, Sierra Leone, and Guinea in a 1:1 allocation ratio to optimized standard of care (oSOC) versus oSOC plus ZMapp. A maximum of 200 subjects were to be randomized (100 per treatment arm) in this trial. The primary endpoint for the trial is survival as assessed at Day 28.

Following the first randomized patient on March 13, 2015, the Data and Safety Monitoring Board (DSMB) reviewed interim data on 7 occasions. Following each review, the DSMB indicated that they had no safety concerns and recommended the study continue. In anticipation of study closure due to the absence of EVD, pooled (both treatment groups combined and blinded) outcome data were provided to the U.S. study team by the unblinded statisticians, [name] and [name], on November 25, 2015. These data were used to update the data analysis plan that was prepared prior to the beginning of the trial. The pooled data were updated on December 31, 2015 following submission of 28 day follow-up data for the last person randomized on November 21, 2015.

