On January 8, 2016, a provisional draft of the updated data analysis plan was shared with the Food and Drug Administration, Mapp Biopharmaceutical, INSERM, and other participating site investigators. The final data analysis plan detailed in the present document considers the comments that were received concerning that January 8th proposal. The document retains some of the information from the original analysis plan concerning the format and content of open and closed DSMB reports.

As of January 14, 2016, 42 days after the last case of EVD in Liberia was discharged, all three countries in West Africa had been declared Ebola-free. Accordingly, the study was planned for closure to new accrual as of that date. Subsequent to that determination there has been a potential resurgence of EVD reported in Sierra Leone; the scope and duration of that recent outbreak, as well as whether any potential new cases may be referred for enrollment, are unclear at this time. If additional enrollments do occur, this will delay the timeline for implementing the final study analysis as summarized in this document. As of the original

planned date of closure on 1-14-2016 there have been a total of 72 patients randomized on the protocol.

3 PLANNED Analyses

Unless otherwise stated, all tables, figures, and listings will show results by randomized arms. For tables with categorical variables, the number (%) will be presented. For tables with continuous variables, the mean, standard deviation, median, 25th and 75th percentiles, min and max will be presented. The number with missing values will also be shown. In calculation of percentages, subjects with missing data will not be included in the denominator. Data presented as listings or figures will be specifically noted.

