3.1 Analysis Populations

The primary population includes all randomized patients, with the exception of one individual who fled from the ETU on the first day. This is the only subject for whom there is missing primary outcome data. (Sensitivity analyses will also be performed including this individual in his/her assigned group, as described below).

The primary analyses will be performed on all subjects regardless of baseline covariates. The study stratified randomization based on cycle threshold (CT > 22 vs. CT \leq 22) and geographic location, and analyses will be presented accordingly. In addition, some analyses will specify age subgroups defined as: adults \geq 18 years vs. children aged <18 years.

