3.9 Secondary Outcomes

Major secondary outcomes:

This section prioritizes the secondary analyses. The study has limited power—the end of the epidemic means the study will close prior to accruing its targeted sample size. As a result, prioritization of secondary endpoints is needed. We also feel it is important to carefully consider the strengths and limitations of the secondary outcomes prior to unblinding. It is recognized that the secondary endpoint analyses described below will be difficult to interpret if the primary analysis does not demonstrate that ZMapp significantly reduces mortality compared to oSOC alone.

Two endpoints are under consideration: time-to-viral clearance (clearance is defined as the first negative PCR result) and time-to-discharge. One could give different arguments for which is a better choice. Time to discharge undoubtedly encompasses several aspects simultaneously: clearance of virus, amelioration of symptoms, etc. However, there is the possibility of a treatment-associated bias in this outcome. For example, if some patients who were given ZMapp were discharged later to make sure there were no drug-related safety issues, then ZMapp may appear less favorable using this endpoint. Also, we have heard reports that patients were kept in a treatment unit after recovery for a variety of reasons, including waiting for discharge kits containing food supplies and other household items or the presence of a relative undergoing treatment for Ebola at the same unit. These issues make time-to-discharge a less precise indication of how a patient feels or functions.

Time-to-viral clearance is a more objective outcome, but it is also not free of problems. Specifically, it is unclear whether this assay was adequately standardized across sites in this study, leading to concerns about measurement variability. Further, samples were taken on half or fewer of participants on many of the days. Nonetheless, failure to measure PCR is likely to have occurred equally in the two arms and the time interval between a positive and negative PCR was within 3 days for 39 of 50 patients (78%) and within 5 days for 47/50 (94%) of patients . Therefore, it is felt that **time to viral clearance should be the more important secondary outcome**, although both outcomes will be analyzed. Note that, for either outcome, death must be taken into account.

1. Viral clearance/death

Unless otherwise stated, viral clearance is defined by the occurrence of a negative PCR.

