3.9.1 Other Secondary Outcomes

In addition to those parameters described in Section 3.6 above, the following will be summarized by treatment group as described:

• Vital Signs: blood pressure, pulse, body temperature, respiratory rate, oxygen saturation – summarized daily by treatment group

• Current symptoms –

Two analyses will be performed to compare the number of symptoms across groups:

- 1. The first analysis of symptoms will compute the average number of symptoms per day during the first 28 days for each patient as well as the average number of days with symptoms. Days with no information on symptoms, including days following the death or discharge of a patient, will be excluded. The groups will be compared using the Wilcoxon rank-sum test. An additional analysis will be conducted using the van Elteren stratified Wilcoxon test on the four strata defined by location (USA/Liberia/Sierra Leone versus Guinea) and cycle threshold (≤22 versus >22).
- The second analysis of symptoms will be identical to the above analysis, but only during the first 3 days. The rationale is that analyses over the entire 28-day period may be difficult to interpret because some patients will be discharged and others may die. Furthermore, the proportion discharged and proportion dying may differ by arm. Restricting attention to the first 3 days will focus the analysis on the initial stage which is free from discharges and some of the deaths.
 - Percent with any symptom
 - Daily summary of number of reported symptoms
 - Summarized for 7 day intervals by treatment group
 - Symptoms at day 28 and day 58 are also summarized.
- Chemistries: measurement of serum creatinine and potassium were required and will be summarized for each 3-day window (i.e. days 1- 3, days 4 6, etc.) by treatment groups, all other chemistries were considered optional and will be summarized as available
 - Additional subgroup analysis will repeat the above for adults and children
 - PCR: blood (note- any CT 40.0 or greater will be treated as negative)
 - \circ summarized for each 3-day window (i.e. days 1- 3, days 4 6, etc.)
 - if more than one PCR is available in a 3 day period for a given subject, the mean result will be used.
 - o summarized as change from baseline for each 3-day window
 - Both of the above will be presented as quantitative (continuous) and qualitative
 - Improvement or worsening of the CT value within the first 72 hours
 - Figure: Kaplan-Meier plot of time to negative Ebola PCR

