 - Kaplan-Meier plot repeated for adults and children
 - Individual PCR curves will be presented
- PCR urine (as available)
 - \circ summarized for each 3-day window (i.e. days 1- 3, days 4 6, etc.) by treatment groups
 - presented as % positive
 - additional separate tables for adults and children
- Hematology, chemistries, and coagulation: optional data summarized as available
 - \circ summarized for each 3-day window (i.e. days 1- 3, days 4 6, etc.)
 - summarized as change from baseline for each 3-day window
 - additional separate tables for adults and children

- Urinalysis: optional data summarized as available
- Imaging and resuscitation: optional data summarized as available

32.1.1

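### The Kaplan-Meier plot of time to negative PCR has no rule for deaths; if deaths are censored, the usual default, it would end at about 100% clearance when 69% to 70% of patients cleared

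*Combined protocol and SAP*

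**What the plan says.** Section 3.9.1 of the Final Data Analysis Plan, under blood PCR, lists "Figure: Kaplan-Meier plot of time to negative Ebola PCR", followed by "Kaplan-Meier plot repeated for adults and children". The opening of section 3 sets the default layout: "Unless otherwise stated, all tables, figures, and listings will show results by randomized arms". The curves are therefore by arm. No sentence says what happens to a patient who dies before a negative PCR.

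Section 3.9 makes time to viral clearance the more important secondary outcome, ahead of time to discharge, defines clearance as the first negative PCR, and adds: "Note that, for either outcome, death must be taken into account". The formal analyses in that section follow this. The rank test gives patients who die within 28 days worse ranks than survivors. The Fisher test counts death together with clearance later than day 10 as failure. The rule is not carried to the plot.

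**The concern.** A patient who dies before clearing can never clear. Death is therefore a competing event, not loss to follow-up. Kaplan-Meier with censoring at death removes the dead from the risk set and implicitly gives them the later clearance experience of the survivors. The curve then estimates clearance in a hypothetical setting without death, while a reader will take it as the proportion of patients who cleared.

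At stake is one descriptive figure. Where mortality differs between arms, censoring inflates the curve more in the arm with more deaths and draws the two curves together. The figure could then look at odds with the rank test of the same outcome.

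**Working it through.** **Inputs**
- Randomized: 72 (section 2: "planned date of closure on 1-14-2016 there have been a total of 72 patients randomized on the protocol").
- Primary population: 71, all randomized patients "with the exception of one individual who fled from the ETU on the first day" (section 3.1). On missing vital status, the same section says: "This is the only subject for whom there is missing primary outcome data".
- Deaths: all within 8 days (section 3.8, baseline risk stratification).
- Clearance times: 49 observed, 13 of them after day 10 (section 3.9, viral clearance analysis B).
- A second count of 50 patients with a positive-to-negative PCR interval (section 3.9).
- Allocation 1:1 (section 2). Arm sizes of 36 and 35 are my assumption.

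**Step 1. The plan's own figures.** 13/49 = 26.5%, 39/50 = 78% and 47/50 = 94%. All three reproduce. The plan gives no clearance percentage for the plot itself.

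**Step 2. Patients who did not clear.** 71 − 49 = 22, or 71 − 50 = 21. The plan does not state the number of deaths in these terms. I infer that these patients are essentially the deaths. The blinded discharge distribution, which also has 49 patients, is consistent with that.

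**Step 3. Proportion cleared.** With vital status known for all 71, cumulative incidence with death as a competing event is the number cleared divided by 71:
- 49/71 = 69.0%
- 50/71 = 70.4%

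**Step 4. Kaplan-Meier with deaths censored at death.** The plotted quantity is 1 − Π(1 − d_j/n_j), where d_j patients clear at time t_j and n_j are still at risk. After day 8 there are no more deaths to censor. After day 10 the risk set is the 13 late clearers. At the last clearance time everyone still at risk clears, so d = n, that factor is 0, and the curve ends at 1 − 0 = 100%. This holds whatever the number of deaths.

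**Step 5. One survivor without a negative PCR.** Take 49 cleared, 21 dead and 1 survivor censored at day 28. If all deaths precede all clearances, the curve ends at 49/50 = 98%. Simulation over assumed times (deaths on days 0–8, 36 clearances on days 2–10, 13 on days 11–28) gives a mean of 97.7% pooled. Single arms average about 98%, with a lowest value of 92%.

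**Step 6. Day 10.** Cleared by then: 49 − 13 = 36, so cumulative incidence is 36/71 = 50.7%. The censored-death Kaplan-Meier estimate lies between 36/71 = 50.7% (all these clearances before any death) and 36/49 = 73.5% (all deaths before any clearance).

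**Step 7. By arm.** Deaths by arm are not in the documents, so the split of 22 deaths is assumed and varied.

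| Deaths, arm 1 / arm 2 | Cleared, arm 1 | Cleared, arm 2 | Censored-death KM end point |
|---|---|---|---|
| 5/36, 17/35 | 31/36 = 86.1% | 18/35 = 51.4% | 100%, 100% |
| 9/36, 13/35 | 27/36 = 75.0% | 22/35 = 62.9% | 100%, 100% |
| 11/36, 11/35 | 25/36 = 69.4% | 24/35 = 68.6% | 100%, 100% |

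In the first row the overstatement is 13.9 points in one arm and 48.6 in the other. A difference of 86.1 − 51.4 = 34.7 points is absent from the end of the curves. The result needs each arm to have a clearance after its last death. With random allocation of the 13 late clearers and at most 25 survivors per arm, the chance that all fall in one arm is at most 2 × C(25,13)/C(49,13), about 0.004%.

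**Step 8. Deaths kept at risk to day 28 as never cleared.** The pooled curve ends at 49/71 = 69.0%, as in step 3. With no other censoring before day 28 the two methods coincide.

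**The case against.** The strongest reply is that the plan never says deaths are censored. Section 3.9.1 sits under section 3.9, whose instruction to account for death could be read as covering the plot, and a product-limit curve that keeps the dead in the risk set would comply. This stands. A reader might infer that the plan prescribes a wrong estimator. The documents show a named estimator with no death rule, whose ordinary default conflicts with the plan's own instruction.

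A reader might also infer that a survival benefit would be hidden from the trial. That is not supported. Mortality is the primary endpoint, Kaplan-Meier mortality plots by treatment group are planned in section 3.8, and both formal clearance analyses count deaths as bad outcomes.

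Nor is this the main display of the main secondary outcome. It is a descriptive item under other secondary outcomes with no test attached, and nothing in the text ties it to the rank test. The displays named with the formal clearance analyses are forest plots.

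Finally, 100% in both arms is not certain. One survivor without a documented negative PCR lowers the end point, and the adult and child curves rest on subgroup counts that the plan does not give.

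What remains is that the default reading produces a wrong clearance proportion, and the plan does nothing to prevent it.

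**Conclusion.** The point holds for this figure. With deaths censored at death, the pooled curve ends at about 100%, or about 98% with one uncleared survivor, against 69.0% to 70.4% who cleared: an overstatement of roughly 27 to 31 points (98 − 70.4 = 27.6; 100 − 69.0 = 31.0). It is larger in the arm with more deaths.

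This rests on three things: deaths being censored, which the plan neither states nor excludes; the blinded pooled counts in the plan; and the inference that those who did not clear are essentially those who died. The difference between 49 and 50 cleared does not matter to the conclusion. The arm-level figures are illustrations over assumed splits. The consequence is a descriptive curve that can mislead. No planned test, p-value or primary conclusion is affected.

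**What to change.** In section 3.9.1, replace the Kaplan-Meier plot with the cumulative incidence of first negative PCR by randomized arm, with death as a competing event (Aalen-Johansen estimator). Showing the cumulative incidence of death alongside would help the reader. An equivalent choice is to keep the plot and state that patients who die stay in the risk set to day 28 as never cleared. Apply the same rule to the adult and child plots, and say how a survivor with no documented negative PCR is censored.

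The cost is one or two sentences in the plan and a different plotting call. It needs no new data, and no test changes.

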3.9.2 Safety-Related Outcomes

- SAEs will be summarized and compared between treatment groups as follows:
 - Number and percent of patients experiencing SAEs by treatment group. Test of statistical significance will use Fisher's exact test.
 - For SAEs that are assessed as related to study drug, counts by treatment groups and p-value from zero-inflated negative binomial model.
- Safety line listings by treatment group will be provided for SAEs and "unanticipated problems". Listings will include treatment group label, diagnosis, relatedness to treatment, date of onset, time from treatment to onset, event status (recovered/resolved, recovering/resolving, not recovered/not resolved, recovered/resolved with sequelae, death), date of resolution or death, and EVD status.
- Unanticipated problems

Incidence of "unanticipated problems" will be tabulated for each of the treatment groups. Reports will have similar format as the summary reports for SAEs.

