Table 11 shows the probability of crossing the boundary and declaring a treatment difference if we begin monitoring after 6 patients per arm and continue monitoring after each additional patient in both arms up to 20/arm, then every 20 per arm up to 100/arm. This probability of crossing the boundary depends on the true mortality probabilities in each arm, but the maximum value when the event probabilities in the 2 arms are equal is approximately 6% for a trial with 100 participants per arm. Even though the Bayesian methodology does not explicitly aim to control the type I error rate, that rate is controlled at close to the conventional level of 0.05. The first 5 rows of numbers in Table 11 also show type I error rate if circumstances beyond our control result in a final sample size of 20, 40, 60, or 80 per arm.

Power and Sample Size

The last 6 rows of numbers in Table 11 show scenarios with event probabilities differing in the 2 arms. With 100 per group, power is 88% to detect a difference if the true mortality probabilities in the 2 arms are 0.20 and 0.40, a 50% relative reduction. The selected sample

size of 100/arm also gives reasonably high power (83%) to detect a difference if the true mortality probabilities are 0.30 and 0.50, a 40% relative reduction.

Table 12shows the average sample size, taking into account the possibility of stopping early, for the scenarios with a treatment effect. If the true mortality rates in arms A and B are 0.3 and 0.5, respectively, and a sample size of 100 is targeted, then the study will stop for efficacy, on average, with only 76 patients (per arm).

Table 10: Flexibility of Trial Design

The top row gives the number of patients per arm, and the boundaries in parentheses are the numbers of deaths in the 2 arms, with + indicating that number or greater (e.g., in the "8" column, 7+ means 7 or 8).

6	7	8	9	10	11	12	13	14	15	16	17	18	19	20
(6 , 0)	(6+,0)	(7+,0)	(7+,0)	(7+,0)	(7+,0)	(7+,0)	(7+ , 0)	(8+,0)	(8+,0)	(8+,0)	(8+,0)	(8+,0)	(8+ , 0)	(4+,0)
	(7,1)	(8,1)	(8+,1)	(8+,1)	(9+,1)	(9+,1)	(9+,1)	(9+,1)	(10+,1)	(10+,1)	(10+,1)	(10+,1)	(10+,1)	(6+,1)
			(9,2)	(9+,2)	(10+,2)	(10+,2)	(10+,2)	(11+,2)	(11+,2)	(11+,2)	(11+,2)	(11+,2)	(12+,2)	(8+,2)
				(10,3)	(11+,3)	(11+,3)	(11+,3)	(12+,3)	(12+,3)	(12+,3)	(13+,3)	(13+,3)	(13+,3)	(9+,3)
					(11,4)	(12,4)	(12+,4)	(13+,4)	(13+,4)	(13+,4)	(14+,4)	(14+,4)	(14+,4)	(11+,4)
						(12,5)	(13,5)	(13+,5)	(14+,5)	(14+,5)	(15+,5)	(15+,5)	(15+,5)	(12+,5)

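### The Final DAP compares all SAEs between arms only by number, percent and a Fisher p-value; adding an interval, for any SAE and for non-fatal SAEs, would show how much harm the data leave open.

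*Combined protocol and SAP*

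**What the plan says.** Section 2 of the Final DAP (January 20, 2016) keeps safety in the primary objective: "The Primary Objective of this study was to establish the safety and efficacy of ZMapp in patients diagnosed with Ebola virus infection".

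Section 3.9.2 then gives one between-arm comparison of all SAEs: "Number and percent of patients experiencing SAEs by treatment group. Test of statistical significance will use Fisher's exact test". Its only other SAE test is narrower and also ends in a p-value: "For SAEs that are assessed as related to study drug, counts by treatment groups and p-value from zero-inflated negative binomial model". Neither line gives an effect estimate, an interval, a significance level or a relevant excess. The general convention at the start of section 3 does not fill the gap: "For tables with categorical variables, the number (%) will be presented".

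Mortality is treated differently. Section 3.8 specifies posterior medians and 95% credible intervals for the relative risk and the risk difference, from independent uniform priors and beta posteriors.

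The point concerns the Final DAP only. The earlier Data Analysis Plan for MCM RCT (4.6.1) also had a rate model for all SAEs and Kaplan-Meier curves with a log-rank test. It also planned 95% intervals for infusion reactions and interruptions (4.6.4, 4.6.5). The Final DAP does not carry these over.

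**The concern.** A test of no difference can show harm if the excess is large enough, but a null result does not bound the harm. Only an estimate with an interval does that. The trial closed early ("there have been a total of 72 patients randomized on the protocol"), so the SAE comparison has about 36 patients per arm. If the p-value is the only between-arm summary beyond counts, the report cannot say how large an excess of serious events on ZMapp remains compatible with the data. That is the question a safety objective asks.

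The any-SAE outcome adds a second problem. It includes every death, so fewer deaths on ZMapp could offset more non-fatal serious events, and the combined comparison could look neutral.

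**Working it through.** **Plan's own figure.** The documents give no power, event rate or detectable excess for SAEs. The nearest stated figure is for mortality at 100 per arm, in protocol section 22: "reasonably high power (83%) to detect a difference if the true mortality probabilities are 0.30 and 0.50". Exact recursion of the planned rule (uniform priors; thresholds 0.999 interim and 0.975 final; looks at 6 to 20, then 40, 60, 80 and 100 per arm) gives 0.834, which agrees.

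**Inputs from the documents.**
- 72 randomized, allocated "in a 1:1 allocation ratio to optimized standard of care (oSOC) versus oSOC plus ZMapp". The split actually reached is not stated.
- 71 in the primary population: "The primary population includes all randomized patients, with the exception of one individual who fled from the ETU on the first day".
- Every death must be reported as an SAE (protocol 26.5.1).
- Section 3.9 of the Final DAP uses denominators of 49 and 50 for viral clearance and 49 for discharge.

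**Floor for the any-SAE risk (an inference).** 71 − 50 = 21 and 71 − 49 = 22 deaths. 21/71 = 29.6% and 22/71 = 31.0%. The pooled any-SAE risk is therefore at least about 30%, so scenarios with any-SAE risks of 10% to 20% do not fit this trial.

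**Power of Fisher's test.** Power = Σᵢ Σⱼ Bin(i; n₁, p₁) · Bin(j; n₀, p₀) · 1{Fisher p(i, j) ≤ 0.05}, summed over all tables. Assumptions: two-sided 0.05 (3.9.2 states neither sidedness nor level) and an oSOC risk of 30%.

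| Excess on ZMapp | 36 v 36 | 35 ZMapp v 36 oSOC |
|---|---|---|
| 10 points (30% to 40%) | 9% | 12% |
| 20 points (30% to 50%) | 31% | 35% |
| 30 points (30% to 60%) | 64% | 67% |

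The reverse split (36 ZMapp v 35 oSOC) lies between the two columns. With an oSOC risk of 40%, the ranges are 8–10%, 29–33% and 64–67%, so the picture does not hinge on exactly 30%. At 36 per arm and a 30% oSOC risk, 80% power needs an excess of about 36 points. With 11 oSOC patients affected, p ≤ 0.05 needs 21 on ZMapp, an observed gap of 10/36 = 28 points. At the planned 100 per arm, power for 30% to 50% would have been 79%.

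**What an interval would show.** By the 3.8 method, each risk has posterior Beta(x+1, n−x+1), and the interval runs from the 2.5th to the 97.5th percentile of the difference. The counts are illustrative.
- 15/35 v 11/36: Beta(16, 21) against Beta(12, 26). Observed difference 42.9% − 30.6% = 12.3 points; Fisher p = 0.33; interval −10 to +33 points.
- 11/35 v 11/36: Beta(12, 25) against Beta(12, 26). Near-equal counts; the upper limit is still about +22 points.

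**Masking by deaths (assumed rates).** Take mortality of 40% on oSOC and 20% on ZMapp, with non-fatal SAEs in 5% and 25% of survivors. Any-SAE risk is 0.40 + 0.60 × 0.05 = 43% on oSOC and 0.20 + 0.80 × 0.25 = 40% on ZMapp. A fivefold difference in non-fatal SAEs among survivors disappears in the combined figure.

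**The case against.** The strongest reply is that the plan never makes this p-value its safety criterion. A reader might infer that the safety objective can be met only by taking p > 0.05 as no difference. Nothing in the documents says so: Final DAP 3.9 acknowledges limited power, and the protocol's benefit section expects any evidence of benefit to be suggestive rather than definitive. That reply stands, and misreporting should not be presumed.

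A reader might also infer that any real excess would probably be missed. That goes too far. A 30-point excess over 30% is found about two times in three, and the documents define no clinically relevant SAE excess against which to judge.

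The safety evidence is also wider than one test. Death has credible intervals and a rule for declaring ZMapp inferior. Line listings, infusion summaries, symptom comparisons and chemistries by arm are planned, and the DSMB raised no safety concern at seven reviews. This too is fair, but none of it estimates the between-arm SAE excess with its uncertainty.

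Finally, any-SAE is dominated by deaths, so its interval would partly repeat the mortality interval. Targeted symptoms need not also be reported as SAEs before discharge (protocol section 26), so SAEs capture toxicity imperfectly. The first part is a reason to report non-fatal SAEs separately. The second is a limit that no interval removes. Readers could compute an any-SAE interval from the tabulated counts, but the plan should specify the analysis that its objective needs.

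**Conclusion.** The point holds for Final DAP 3.9.2 as a cheap improvement. The only planned between-arm comparison of all SAEs carries no estimate of effect and no interval. At about 36 per arm and an oSOC risk near 30%, a non-significant result is expected roughly two times in three under a true 20-point excess, and about nine times in ten under a 10-point excess. It therefore carries little information about harm.

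This rests on an inferred death count, an assumed oSOC risk, an assumed two-sided 0.05 level and an assumed near-equal split. It does not show that the plan will claim safety from a null test, that excesses of 30 points would usually be missed, or that no SAE has an interval, since death does.

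**What to change.** In Final DAP 3.9.2, add the risk difference and relative risk (ZMapp against oSOC) with 95% credible intervals by the beta-posterior method of 3.8. Give them for patients with any SAE and separately for patients with a non-fatal SAE. State that the safety conclusion rests on the upper limit, that is, on the largest excess the data leave open, and that a non-significant p-value is not evidence of safety. Fisher's p can stay as a secondary figure.

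The cost is a paragraph of text and a few table lines, using a method already specified for the primary outcome and needing no new data. The safety statement will probably be less favourable, because the upper limit is likely to allow an excess of about 20 points or more. The interval makes the low information visible; it does not restore power.
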